8.2 AE/SAE Intensity and Relationship Assignment

- AE/SAE Intensity

The investigator must rate the intensity for all AEs that occur during the study using the grades based on CTCAE (v4.03) provided below:

- Grade 1 (Mild):

Asymptomatic or mild symptoms; clinical or diagnostic observations only; intervention not indicated.

- Grade 2 (Moderate):

Minimal, local or noninvasive intervention indicated; limiting age-appropriate instrumental ADL*.

- Grade 3 (Severe or medically significant but not immediately life-threatening):
Hospitalization or prolongation of hospitalization indicated; disabling; limiting self-care ADL**.
- Grade 4 (Life threatening consequences):
Urgent intervention indicated.
- Grade 5 (Death related to AE)

Note: Activities of Daily Living (ADL)

*Instrumental ADL refer to preparing meals, shopping for groceries or clothes, using the telephone, managing money, etc.

**Self-care ADL refer to bathing, dressing and undressing, feeding self, using the toilet, taking medications, and not bedridden.

Adverse events observed during the study will be coded using Medical Dictionary for Regulatory Activities (MedDRA) and will be reported by dose level and overall by System/Organ/Class (SOC) classified in MedDRA as appropriate.

- AE/SAE Relationship Assessment

The investigator will be asked to assess all AEs with respect to their causal relationship to the study drug according to the following classification:

- Definitely Related

There is clear evidence to suggest a causal relationship, and other possible contributing factors can be ruled out. The clinical event, including an abnormal laboratory test result, occurs in a plausible time relationship to study

agent/intervention administration and cannot be explained by concurrent disease or other drugs or chemicals. The response to withdrawal of the study agent/intervention (dechallenge) should be clinically plausible. The event must be pharmacologically or phenomenologically definitive, with use of a satisfactory rechallenge procedure if necessary.

■ Probably Related

There is evidence to suggest a causal relationship, and the influence of other factors is unlikely. The clinical event, including an abnormal laboratory test result, occurs within a reasonable time sequence to administration of the study agent/intervention, is unlikely to be attributed to concurrent disease or other drugs or chemicals, and follows a clinically reasonable response on withdrawal (dechallenge). Rechallenge information is not required to fulfill this definition.

■ Possibly Related

There is some evidence to suggest a causal relationship (e.g., the event occurred within a reasonable time after administration of the trial medication). However, the influence of other factors may have contributed to the event (e.g., the subject's clinical condition, other concomitant events). Although an adverse drug event may rate only as "possible" soon after discovery, it can be flagged as requiring more information and later be upgraded to probable or certain as appropriate.

■ Unlikely

A clinical event, including an abnormal laboratory test result, whose temporal relationship to study agent/intervention administration makes a causal relationship improbable (e.g., the event did not occur within a reasonable time

after administration of the trial medication) and in which other drugs or chemicals or underlying disease provides plausible explanations (e.g., the subject's clinical condition, other concomitant treatments).

■ Not related

The AE is completely independent of study agent/intervention administration, and/or evidence exists that the event is definitely related to another etiology.

There must be an alternative, definitive etiology documented by the clinician

Expected Events Related to Disease Process: Provide explicit definitions of the type(s), grade(s), and duration(s) of adverse event(s) that will be considered disease related.

8.3 Collecting, Recording and Reporting of Adverse Events

8.3.1 Collecting and Reporting of AE

AEs may be volunteered spontaneously by the study subject, discovered as a result of general questioning by the study staff, or determined by physical examination. All AEs will be recorded on the CRF. For all AEs, the investigator must pursue and obtain adequate information both to determine the outcome of the AE and to assess whether it meets the criteria for classification as a serious AE requiring immediate notification. AEs should be reported starting from signing ICF to the end of study (Visit 12) or to the last visit patients finish before withdrawal. Follow-up of the AE, even after the date of study drug discontinuation, is required if the AE persists. The study subject will be followed until the event resolves or stabilizes at a level acceptable to the investigator.

8.3.2 Reporting of SAE

Serious, alarming and/or unusual adverse events must be reported to the sponsor/CRO contact within 24 hours of the investigator's knowledge of the event. Any event requiring hospitalization (or prolongation of hospitalization) that occurs during the course of a subject's participation in a clinical study must be reported as a serious adverse event, except hospitalizations for the following:

- Social reasons in absence of an adverse event
- Surgery or procedure planned before entry into the study (must be documented in the CRF)

The investigator is responsible to communicate details of medical emergencies in trial subjects to the Ethics Committee. Reporting of adverse events will comply with US federal regulations, Japanese regulations and Taiwanese regulations for IND safety reporting. Sponsor/CRO is responsible to inform the events to FDA, PMDA and TFDA.

Fatal or life-threatening, suspected unexpected ADRs should be notified to Local ADR Reporting Center by sponsor/CRO as soon as possible, but no later than 7 calendar days, after first acknowledged by the sponsor, and a complete report should be followed 8 additional calendar days. This report must include an assessment of the importance and implication of the findings and/or previous experience on the same or similar medical products. Serious, unexpected ADRs that are not fatal or life-threatening must be filed as soon as possible but no later than 15 calendar days after first acknowledged by the investigator that a case qualifies.

The information which sponsor/CRO evaluates as threatening the safety of the subject and having impact on the ongoing study should be urgently (as soon as possible and within 1 business day following the information receipt date) transmitted to the investigators/trial sites via e-mail, etc. from the study monitor or person responsible for monitoring out of the safety information to be reported to the regulatory authority. In unexpected serious adverse events to be reported to the regulatory authority, the information which sponsor/CRO considers to be highly emergent safety information (per case) should be transmitted to the investigators/trial sites within 30 days following the information receipt date. Other serious events to be reported to the regulatory authority should be transmitted to the investigators/trial sites as monthly periodic report or annual report within 30 days following the transmission request date via e-mail, etc. from the study monitor or person responsible for monitoring.

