In Phase I proportion, eligible patients will be recruited sequentially with one week staggering in the initiation of study treatment. Eligible patients will also be randomized into 1:1 ratio into one of Treatment (TWB-103+Tegaderm™) and Control (placebo+Tegaderm™) groups. Phase I plan to recruit 3 evaluable TWB-103+Tegaderm™ treated and 3 evaluable placebo+Tegaderm™ treated patients. Patients in phase I are considered as evaluable when (1) he/she receives at least one dose and has follow-up evaluation at least 14 days after first dose or (2) he/she receives at least one dose and has early withdrawn due to safety reasons before Day 28. When all of those 6 evaluable patients complete the planned treatment period (14 days or till first 100% re-epithelialization, which comes first), the recruitment of patients will be temporarily stopped for 14 days for safety observation. The safety data of TWB-103 before and on Day 28 Visit will be reviewed by the sponsor and the principal investigator. If no safety issue of TWB-103 is decided, the study will enter Phase II portion and eligible patients will be randomized into 1:1 ratio into one of Treatment and Control groups.

Each patient will have treatment for up to 14 days or to the day of 100% re-epithelialization, whichever comes first. Patients assigned to the Treatment Group will receive TWB-103 add-on Tegaderm™ till 100% re-epithelialization or up to 10 days,

whichever comes first and will receive Tegaderm™ alone from Day 10 to Day 14 if re-epithelialization can not be attained by Day 10. Patients assigned to the Control Group will receive placebo+Tegaderm™ till 100% re-epithelialization or up to 10 days, whichever comes first and will receive Tegaderm™ alone from Day 10 to Day 14 if re-epithelialization can not be attained by Day 10. Patients from either group (treatment or control) will have application of Tegaderm™ alone up to Day 28 if 100% re-epithelialization of DSWs is not observed on Day 14 (end of treatment).

Patients will be required to attend scheduled visits at Screening, Day 0 (treatment start day), Day 3, Day 7, Day 10, Day 14 (end of treatment). In case patients achieve 100% re-epithelialization before or at Day 10, patients will finish up the assessments on the day with 100% re-epithelialization. This day of 100% re-epithelialization will be the end of treatment and the remaining scheduled treatment visits, if applicable, will be dismissed.

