4.3 Stopping rules and unscheduled visits

4.3.1 Stop the study

The study will be stopped when > 1/3 of patients in the phase I have developed study drug related grade 2 or above SAEs defined as in Section 8. The investigator will determine if SAEs are study drug related without breaking the blind. If the cause of SAE is inconclusive, the investigator can request to break the blind following the procedure stated in Section 4.2.

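### The protocol's first two rules for sending safety information to sites overlap, and the 'highly emergent' single-case rule allows 30 days, longer than either regulator deadline.

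*Combined protocol and SAP*

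**What the plan says.** Section 8.3.2 (Reporting of SAE) sets three classes of sponsor-to-site communication.

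1. The first is defined by judgement: "The information which sponsor/CRO evaluates as threatening the safety of the subject and having impact on the ongoing study". It is to be "urgently (as soon as possible and within 1 business day following the information receipt date) transmitted to the investigators/trial sites".
2. The second opens with "In unexpected serious adverse events to be reported to the regulatory authority" and covers what the sponsor/CRO regards as highly emergent in such events. Its limit reads: "highly emergent safety information (per case) should be transmitted to the investigators/trial sites within 30 days following the information receipt date".
3. Other reportable serious events go to sites in monthly or annual reports, within 30 days of the transmission request date.

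The same section sets the outward clocks. Fatal or life-threatening suspected unexpected reactions are notified "as soon as possible, but no later than 7 calendar days" after the sponsor first learns of them, with a complete report 8 days later. Other serious unexpected reactions have 15 calendar days, counted from the investigator's acknowledgement that the case qualifies. Investigators must report serious events to the sponsor/CRO within 24 hours.

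Section 1.2.4 calls the study first-time-in-human for TWB-103. Section 4 describes a multi-center trial in Taiwan and Japan. In Phase I, which plans 6 evaluable patients (3 per group), "eligible patients will be recruited sequentially with one week staggering in the initiation of study treatment". Section 10.2.4 states that there will be no DSMB.

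**The concern.** A class labelled highly emergent would be expected to have a short clock. Here it has the same number of days as the routine periodic reports, although counted from a different date, and more days than the protocol allows for telling the regulator about the same kind of event. The label is undefined and no order of precedence is given, so two people applying the section in good faith could send the same case after 1 business day or after 30 days.

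What is at stake is what investigators at other sites know. Until the information reaches them, they may screen, consent and treat patients, and judge the relatedness of their own events while blinded, without knowing of an unexpected serious case elsewhere. With no DSMB, transmission by the sponsor/CRO is the only route to them that section 8.3.2 describes.

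**Working it through.** No sample size, power or error rate is involved. The check compares the stated limits and then counts treatment starts.

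**Step 1. Site limit against regulator limits** (all in section 8.3.2).

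- Fatal or life-threatening: 30 − 7 = 23 days.
- Other serious unexpected: 30 − 15 = 15 days.

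The clocks start at different points: the sponsor's awareness for the 7 days, the investigator's acknowledgement for the 15, and information receipt for the 30. If the investigator's acknowledgement starts both the 15-day clock and the 24-hour report, sponsor receipt falls at most 1 day later. The site limit then falls on day 30 or 31 and the regulator limit on day 15, a gap of 15 to 16 days. If the acknowledgement comes after the sponsor already has the information, the gap is shorter. Both figures are therefore approximate.

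**Step 2. Phase I starts inside each window.** The protocol gives no accrual rate. I assume the fastest schedule the stagger permits, with no additional patients: six starts on Days 0, 7, 14, 21, 28 and 35. For information received on Day r and a window of w days, count the starts s with r < s ≤ r + w. The index event is in the first patient, received on Day 1 (early) or on Day 6 (just before the second start).

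| Window w (days) | Received Day 1 | Received Day 6 |
|---|---|---|
| 1 | 0 | 1 |
| 7 | 1 | 1 |
| 15 | 2 | 3 |
| 30 | 4 | 5 |

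For w = 30 and r = 1, the starts on Days 7, 14, 21 and 28 fall by Day 31. For r = 6, the start on Day 35 is added, because the window runs to Day 36. Treating 1 business day as 3 calendar days, to allow for a weekend, leaves the first row at 0 and 1. An index event later in Phase I leaves fewer starts to count.

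**Step 3. How many would be active.** With exactly 3 patients per group and the index patient on TWB-103, 2 of the other 5 are on TWB-103. The expected number of active starts is 4 × 2/5 = 1.6 to 5 × 2/5 = 2.

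**The case against.** The strongest reply is that the dangerous case is already covered. The 1-business-day class draws on all safety information reportable to the regulator, and an event bearing on whether the next Phase I patient should be treated would be expected to meet its test. Thirty days is only an outer limit, so a case fitting both descriptions complies with both sentences only if sent within 1 business day. The words 'per case' may simply separate individual reports from periodic ones. These points stand, and they confine the problem to cases the sponsor does not also place in the first class. They do not remove it: that class requires two judgements together, its boundary with highly emergent cases is not drawn, and the 30-day limit still exceeds both regulator deadlines.

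A reader might infer three stronger things, none of which the documents support.

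- That urgent single cases are expressly assigned to the 30-day class and kept out of the 1-day class. Section 8.3.2 contains no such exclusion.
- That a new patient will start every week. The stagger sets the fastest permitted pace, not a rate.
- That the rule in section 4.3.1, "The study will be stopped when > 1/3 of patients in the phase I have developed study drug related grade 2 or above SAEs", depends on letters to sites. The sponsor/CRO receives every serious event within 24 hours, and nothing in the section makes the rule wait for site notification.

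Section 8.3.2 also binds adverse event reporting to US, Japanese and Taiwanese rules. Their content is not in the documents, so whether they impose a shorter limit in practice cannot be judged here.

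**Conclusion.** The concern holds in a limited form. The first two classes overlap without a definition or an order of precedence. For cases left in the second class, sites may be told roughly 15 days (other serious unexpected) or 23 days (fatal or life-threatening) after the regulator's deadline.

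The count of 4 to 5 later Phase I starts is a worst case. It assumes the fastest accrual, an index event in the first patient, a case kept out of the 1-business-day class and use of the full 30 days. It bears on uninformed investigators only to the extent that the later patients are at other sites, because the reporting site and the sponsor already know. The figure bounds the exposure and does not predict it. The point is worth correcting because the limit is a stated rule in a first-in-human, multi-center trial without a DSMB, and correcting it costs little.

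**What to change.** Amend section 8.3.2 so that its regulator and site clocks agree:

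- Define 'highly emergent' and say how it differs from the 1-business-day class.
- State that the shorter limit governs when a case fits both descriptions.
- Require that single-case reports of unexpected serious events reach all sites no later than they reach the regulator.
- Leave the periodic reports' own 30-day clock, from the transmission request date, as it is.

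No new condition on the staggered starts is needed. On the worst-case schedule above, the third change would reduce the later starts inside the window from 4 or 5 to 1 under the 7-day deadline, or 2 to 3 under the 15-day deadline, treating those deadlines as running from sponsor receipt.

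The cost is protocol wording and an e-mail per case by the route the section already names. The downside is a few more safety letters.

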8.3.3 Reporting of Pregnancy

Any patient or patient's partner who becomes pregnant during the treatment period should be recorded and the information regarding this pregnancy should be collected. Any pregnancy occurs during the 30 days following the last dose of investigational product should also be reported and accompanied information should also be collected. When female patient or male patient's partner suspects a pregnancy during the treatment period or within 30 days of the last dose, a pregnancy test should be conducted. Once pregnancy is confirmed, the patient should stop the administration of investigation product

immediately, if patient is still during the treatment period. The pregnancy should be reported to the sponsor using the pregnancy report form. The Obstetrician/Gynecologist of the female patient or male patient's partner should be notified the trial information. Because information of specific tests regarding this investigational product is not clear yet, whenever possible, a pregnancy should be followed to term or to any premature terminations reported. Additionally, the status of the mother and child should be reported to the sponsor after delivery. Although pregnancy occurring during the trial is not considered as an adverse event, any pregnancy complications should be recorded as AEs or SAEs.

9. DATA ANALYSIS

9.1 Data Quality Assurance

The PI/CRO will provide paper CRFs or electronic CRFs (via EDC system) for the recording and collection of subject data and for the collection of data. All CRFs will be completed as soon as possible after the subject's visit. Corrections to data on the CRFs will be documented or traced. The investigator will review CRFs to indicate that, to his/her knowledge, they are complete and accurate. If further changes are made after this, the investigator will need to again sign the investigator signature page or approve electronically. Designated source documents will be signed and dated by the appropriate study personnel.

9.2 Clinical Data Management

The investigator must agree to complete and maintain source documents and CRFs for each subject participating in the study.

The sponsor/CRO will be responsible for the processing and quality control of the data. Data management will be carried out as described in the sponsor/CRO's standard operating procedures (SOPs) for clinical studies.

The handling of data, including data quality control, will comply with regulatory guidelines and the sponsor/CRO's SOPs as well as provisions of the study-specific Data Management Plan if any.

10. SAMPLE SIZE AND STATISTICAL METHODS

10.1 Determination of Sample Size

The target number will be up to 30 evaluable subjects. Approximately up to 36 patients **will** be **recruited** and to complete a total of 30 evaluable patients. In this study, evaluable population will be per-protocol (PP) population defined in Section 10.2. The determination of sample size is arbitrary as **there** is no historical data can be referred.

10.2 Statistical and Analytical Plans

10.2.1 Analysis Population

Two populations will be introduced for statistical analysis:

Intent-to-treat (ITT) population:

- Patients randomized
- Patients ever treated by at least one dose of trial medication
- Patients with any post-treatment evaluation

Per-protocol (PP) population:

- Dosed with planned dosing regimen of investigational product
- With efficacy endpoint measurement at wound assessment (with first 100% re-epithelialization or complete Day 14 visit evaluation)
- Fulfilling all inclusion and exclusion criteria
- Without taking prohibited medication

Since the dosing regimen designed in Phase I are exactly those designed for Phase II, and the procedures/schedules of assessment that patients receive are

identical in both phases, the data collected in Phase I portion will be combined with those in the Phase II portion for statistical analysis.

Primary endpoints and secondary efficacy endpoints in Phase I/II will be analyzed on ITT and PP population. Non-primary safety endpoints, demographics and baseline characteristics will be analyzed on ITT population. Conclusion of primary endpoint in Phase I will be made based on ITT population analysis results and that in Phase II will be made according to the result of ITT population analysis.

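### No all-treated safety set is defined, and the Phase I primary safety endpoint is also run on the per-protocol set, which can drop patients stopped for a reaction

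*Combined protocol and SAP*

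**What the plan says.** Section 10.2.1 opens with "Two populations will be introduced for statistical analysis", and the Protocol Summary says the same. Neither set is a safety set.

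- **ITT** has three bullets: "Patients randomized", "Patients ever treated by at least one dose of trial medication" and "Patients with any post-treatment evaluation". They are not expressly joined, but only a joint reading gives a usable set.
- **PP** requires, among other things, "Dosed with planned dosing regimen of investigational product" and "With efficacy endpoint measurement at wound assessment (with first 100% re-epithelialization or complete Day 14 visit evaluation"). It also requires that eligibility was met and that no prohibited medication was taken.

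On use of the sets, the section says "Primary endpoints and secondary efficacy endpoints in Phase I/II will be analyzed on ITT and PP population", and then "Non-primary safety endpoints, demographics and baseline characteristics will be analyzed on ITT population". It adds that the conclusion on the primary endpoint, in each phase, is drawn from ITT. It does not say whether safety is tabulated by product received or by product assigned.

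Section 2.2.1 makes the incidence of treatment-related AEs and SAEs, with infections and bleeding named, the Phase I primary endpoint. Section 2.2.2 lists the same incidence as a secondary safety endpoint for Phase I+II.

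**The concern.** A safety analysis should count everyone exposed. A per-protocol set selects on what happened after exposure, and here some of its conditions can fail because of the adverse event being counted. The patients most likely to leave PP include those with the more serious reactions, so the remaining incidence is too low whenever that happens.

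The setting makes each patient count. Section 1.2.1 describes first use in humans, Section 4 plans three evaluable patients per arm in Phase I, and Section 10.2.4 provides no independent monitoring board. A supplementary PP table showing no related events could be read as reassurance when the event patient has simply been removed from it.

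There is a second, smaller gap. Because the ITT set also demands a post-treatment evaluation, no set holds all dosed patients. The same condition, together with the dosing condition, means the set is not intention-to-treat in the usual sense, although the Phase I+II efficacy conclusion rests on it.

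**Working it through.** The plan gives no figure to reproduce here. The check sets the definitions side by side and adds a small illustration.

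**Step 1: is a PP safety analysis planned?** The Phase I primary endpoint is a safety endpoint (Section 2.2.1). Section 10.2.1 puts primary endpoints on ITT and PP without separating safety from efficacy. Read literally, yes.

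**Step 2: how can a patient with a related event fail PP?**

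| PP condition | How the event can break it | What limits it |
|---|---|---|
| Planned regimen given | Section 4.3.2 ends application after an allergic reaction above Grade 2, and allows it to end for a donor-site infection before Day 10. Application is at Visits 2 to 4, i.e. Days 0, 3 and 7 (Section 6.10). | A stop after Visit 4 misses nothing. The Protocol Summary describes two to three applications, so a stop after two is not clearly a breach. |
| Healed, or Day 14 evaluation complete | A patient who leaves before Day 14 unhealed fails. For those who stay, Sections 4.3.2 and 10.2.2 discard wound assessments made after onset; whether Day 14 then counts is not stated. | A patient who stays and attends Day 14 may still qualify. |
| No prohibited medication | Section 4.3.2 allows treatment of the reaction. If that treatment is on the Section 3.6 list, the patient fails, whatever the dosing. | Depends on the treatment used. |

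**Step 3: compare with the Phase I evaluability rule.** Section 4 counts as evaluable a dosed patient who withdrew before Day 28 for safety reasons. PP would generally drop a patient of this kind who left before Day 14 unhealed. The two rules treat the same patient in opposite ways.

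**Step 4: illustrate the Phase I effect.** Inputs: n = 3 in the TWB-103 arm (Section 4); k = number stopped early for a related reaction who fail PP (assumed); no other related events.

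- Incidence among dosed patients = k/3; incidence in PP = 0/(3 − k).
- k = 1: 1/3 = 33% against 0/2 = 0%. Exact 95% intervals are 0.8% to 91% and 0% to 84%.
- k = 2: 2/3 = 67% against 0/1 = 0%.

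The intervals show that neither estimate is precise. The point is the direction of the shift: the event leaves both numerator and denominator.

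**Step 5: the evaluation condition in ITT.** Assume 36/2 = 18 dosed per arm and one dosed patient with no post-treatment evaluation.

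- If that patient is one of four with an event: 4/18 = 22.2% among all treated, 3/17 = 17.6% on ITT.
- If that patient has no known event and three others do: 3/18 = 16.7% among all treated, 3/17 = 17.6% on ITT.

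The shift is small and can go either way.

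**The case against.** The strongest reply is that no decision rests on PP safety. Section 10.2.1 draws the Phase I conclusion from ITT. Section 4 bases entry to Phase II on a review of safety data up to Day 28, and the stopping rule in Section 4.3.1 counts patients in Phase I, not PP patients. This stands, and it limits the point to a supplementary result.

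Three stronger readings might be inferred, and the documents support none of them.

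- *PP removes everyone who had the event.* It does not. A related event that neither stops product, causes early departure nor leads to prohibited treatment leaves the patient in PP. Planned dosing regimen is not defined for a stop that the protocol itself directs.
- *The pooled Phase I+II safety comparison is distorted in the same way.* In the pooled trial this incidence is a secondary safety endpoint (Section 2.2.2), and Section 10.2.1 puts non-primary safety on ITT only. An example built on 15 dosed per arm would also be wrong, because 15 is the per-protocol target (Section 3.1); 36 recruited 1:1 is about 18 per arm.
- *Dosed patients will routinely vanish from safety denominators.* The condition is any evaluation, not an efficacy evaluation. AE recording is already listed after application on Day 0 (Section 7.2), and Section 3.4 asks patients withdrawn before Day 28 to complete that visit's assessments. Such a patient should be rare.

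It can also be said that, apart from the evaluation condition, the ITT set already works as a treated-patient set. That is true, and it is why the repair is small. It does not justify a safety table on PP.

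**Conclusion.** The point holds in limited form. The plan has no all-treated safety set and, read literally, produces a PP version of the Phase I primary safety endpoint from which patients can be removed because of their reaction. Where that happens the PP result is biased towards no harm: 33% against 0% if one of three TWB-103 patients is affected. That count is an assumption. How often it would occur depends on when the product is stopped, on how planned dosing regimen is read, and on what the patient receives for the reaction. Section 10.2.2 itself expects more treatment-related SAEs in the TWB-103 arm, so losses may be unequal between arms.

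The Phase I conclusion is protected because it rests on ITT, and the evaluation condition in ITT should matter little in practice. The change is still worth making for a first-in-human product, since it removes an exclusion that depends on the outcome. The inaccurate ITT label alone would not carry the point. Sample size and significance level are unaffected.

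**What to change.** In Section 10.2.1 and the matching part of the Protocol Summary:

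1. Add a safety set: every patient given at least one application of TWB-103 or placebo, analysed by product received, with no evaluation condition.
2. Use it for every safety endpoint, primary and secondary, including the Phase I primary conclusion.
3. Restrict PP to efficacy endpoints.
4. Call the present ITT set modified ITT, and report by arm the randomised patients it leaves out, with reasons.

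The cost is analysis wording and one additional population flag. No visit, assessment, sample size or aspect of patient management changes.
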